Chief Investigator	[name]. med. [name]
REC number	
Medical condition under investigation	Critical illness
Purpose of clinical trial	To investigate if two devices to monitor and capture Heart Rate Variability (HRV) and ECG data in Critically ill patients produce comparable results.
Primary objective	To describe the robustness of data on HRV obtained by two different monitoring systems during daily care of critically ill patients.
Secondary objective	
 1. To identify the most suitable and cost-efficient device for HRV monitoring in critically ill patients. 2. To define amendments in data capture and analysis required to proceed to a larger clinical trial
Number of Subjects	30 patients

Trial Design	Prospective observational feasibility study
Endpoints	
Primary outcome:
 
 • Number of interpretable HRV epoch episodes for each device and comparison between Isansys device and gold-standard holter monitoring (Isansys and Holter Monitor) 
Secondary outcomes:
 
 • Correlation of HRV time domain, frequency domain and non-linear HRV measures analysis between Isansys wireless monitoring patch and Holter monitoring • Correlation between HRV and onset of arrhythmias • Correlation between HRV and cardiorespiratory events (desaturation, drop in blood pressure >20%, change in ventilator settings) • Nurses' and medical staff's perception of the usability of both monitoring systems in daily routine practice
Main inclusion and Exclusion Criteria	
Inclusion criteria:
 
 • Adult patients ≥18 years • Expected stay in the ICU >48 hours • Sinus rhythm on ITU admission • Mechanically ventilated patients 
Exclusion criteria:
 
 • Non-ICU patient • History of Atrial Fibrillation • Inability to obtain consent
Randomization	Not applicable
Study procedure	
If all inclusion criteria are met and no exclusion criteria are present, patients will be eligible, invited to participate and informed consent will be sought.
 
Continuous ECG data will be recorded using two different devices. ECG data will then be processed to derive HRV using the methodology

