Whilst both monitoring devices are capable of recording continuous ECG and HRV data, it remains unclear how robust the data are with regards to interference and artefacts. In particular, it is unclear how each monitoring device will operate whilst patients are undergoing daily care maneuvers such as physiotherapy, washing and patient repositioning. Furthermore, it has not been described yet how HRV is affected by interventions such as mechanical ventilation, administration of inotropes or vasopressors, paralysis agents, or renal replacement therapy. The current study aims to elucidate the impact of these standard interventions on HRV and the robustness of HRV measurement between the Isansys wireless monitor and the gold-standard HRV monitoring technique. This feasibility study will aide decision making with regard to which device will be most suitable for further studies of HRV in critically unwell patients.

2. Trial Objectives, Design and Statistics

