2.1 Trial objectives

The **primary objective** is:

- To describe the robustness of data on HRV data obtained by two different monitoring systems in daily care of critically ill patients. The Isansys wireless monitoring device will be compared to the gold-standard holter monitoring device for ECG analysis.

The **secondary objectives** are:

- To identify the most suitable and cost-efficient device for HRV monitoring in critically ill patients.
- To define amendments in data capture and analysis required to proceed to a larger clinical trial
- To generate preliminary data on the variation of HRV in a critical care patients.

Primary outcome:

- Number of interpretable monitoring epochs in each HRV monitoring system after elimination of artefacts, extra beats and interference

Secondary outcomes:

- Correlation and comparison of HRV time, frequency and non-linear measures between the Isansys monitoring device and the gold-standard holter monitoring system.
- Correlation between HRV and onset of arrhythmias (ventricular or atrial)
- Correlation between HRV and cardiorespiratory events that commonly occur in critically ill patients, including, oxygen desaturation (SaO₂<85%), variations in blood pressure of >20%, change in ventilatory support, muscle paralysis, position of the patient, administration of vasopressors (e.g. noradrenaline and vasopressin).
- Nurses' and medical staff's perception of the usability of both monitoring systems in daily routine

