2.3 Trial Statistics

ECG data will be downloaded from the holter device and analysis in holter device software package which derive HRV data. RR interval data from the Isansys patch will be downloaded onto an Excel spreadsheet. The RR interval will be uploaded to Matlab. The Medical Engineering and Clinical Physics department have developed a program in the Matlab environment for analysis and output of HRV data. ECG data will undergo preprocessing to remove artefacts and ectopic beats and be analysed using the Ornstein-Uhlenbeck third-order Gaussian process applied to the heart rate/RR interval.¹¹ This technique has been developed by the Medical Engineering and Clinical Physics department. Once the ECG has been preprocessed heart rate variability will be derived according to the European Society of Cardiology guidelines.²

We will use time domain measures, frequency domain measures and non-linear measures such as the poincare plot, approximate and sample entropy and detrended fluctuation analysis in our analysis of HRV.

Comparison between devices will be assessed by Bland-Altman methodology. The difference between measures recorded from the Holter monitor and the Isansys wireless monitor will be plotted against the average value for each HRV measure for individual patients. Any measure of relationship between the measurement error and the estimate of the true value (average of the two measurements) can be examined. If the difference between the Isansys monitor and the holter monitor is sufficiently small not to cause problems in the clinical interpretation (within 95% limits of agreement), then the Isansys wireless device can be considered to be interchangeable with the gold-standard holter monitoring device.

Heart rate variability data will be analysed statistically as described. Descriptive statistics showing means \pm standard deviation (SD) for continuously distributed variables, and number and proportions for categorical variables will be used for all comparisons. Chi-square tests will be used for categorical outcomes unless assumptions of the test are found to have been violated, in which case Fisher's exact test will be used.

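### The interchangeability rule uses HRV differences only and leaves out the primary outcome, interpretable epochs, so a device-level claim could be made despite heavy Isansys data loss

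*Protocol*

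**What the plan says.** **Question.** The synopsis gives the purpose as "To investigate if two devices to monitor and capture Heart Rate Variability (HRV) and ECG data in Critically ill patients produce comparable results". The primary objective in section 2.1 is "To describe the robustness of data on HRV data obtained by two different monitoring systems in daily care of critically ill patients". The Introduction explains why this is open: "it is unclear how each monitoring device will operate whilst patients are undergoing daily care maneuvers".

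**Primary outcome.** Section 2.1: "Number of interpretable monitoring epochs in each HRV monitoring system after elimination of artefacts, extra beats and interference". The synopsis adds a comparison: "Number of interpretable HRV epoch episodes for each device and comparison between Isansys device and gold-standard holter monitoring". Neither place gives a threshold or says what conclusion a good or poor count would support.

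**Rule.** Section 2.3 sets up a Bland-Altman analysis in which the Isansys-Holter differences "will be plotted against the average value for each HRV measure for individual patients". The condition placed on these differences is that they be "sufficiently small not to cause problems in the clinical interpretation (within 95% limits of agreement". When that condition is judged to be met, the protocol draws this conclusion: "then the Isansys wireless device can be considered to be interchangeable with the gold-standard holter monitoring device". The synopsis repeats the rule. Artefacts and ectopic beats are removed before HRV is derived (sections 2.3 and 4.3).

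**The concern.** The rule reaches a conclusion about the device but takes as input only the HRV values that the device managed to deliver. The study asks how well each system holds up against interference and bedside care. Its direct measure of that is the share of the recording that can be used, and this measure cannot block the declaration.

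At stake is the wording of the result. A report could state that the Isansys is interchangeable with the Holter and, elsewhere, that much of its recording was unusable. Both statements would follow the protocol. A reader planning a larger trial could carry away the first without the second. How the agreement limit itself is set is a separate matter: even with a sound clinical margin, the rule would not contain yield.

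**Working it through.** The plan gives no figure to reproduce on this point: no agreement margin, no error SD and no minimum yield. The check is therefore first one of text.

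**Step 1. What enters the rule.**

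| Element | Where | Variable | Conclusion attached |
|---|---|---|---|
| Primary outcome | 2.1, synopsis | Interpretable epochs per device | None |
| Agreement analysis | 2.3, synopsis | Difference in each HRV measure | Interchangeable device |
| General descriptive statistics and tests | 2.3, synopsis | Not tied to epochs | None |
| Choice of suitable, cost-efficient device | 2.1 (secondary objective) | Not specified | No written rule |

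An epoch-level difference needs a value from both devices. An epoch rejected on either side drops out of the comparison and is not counted against agreement.

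**Step 2. Available epochs.** With 5-minute epochs (4.3), 24 h gives 24 × 60 / 5 = 288. The Holter records for 72 h (6.2): 3 × 288 = 864. The Isansys records for up to 5 days (6.2): 5 × 288 = 1,440. Raw counts therefore have different ceilings, and a yield comparison needs a percentage over the shared window.

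**Step 3. Illustration only.** Assumptions, none from the protocol: log-scale HRV, within-patient epoch SD 0.3, error SD 0.1 per device, no bias, 864 epochs, Holter keeps 95%, Isansys loss at random.

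- *Epoch-level limits*: 1.96 × √(0.1² + 0.1²) = ±0.277. Yield is not in the formula.
- *Per-patient means over shared epochs*: 0.277 / √(number shared). At 95% kept, 864 × 0.95 × 0.95 = 780 shared, giving ±0.010. At 10% kept, 864 × 0.95 × 0.10 = 82 shared, giving ±0.031.
- *Per-patient means over each device's own epochs*, with n_I and n_H epochs kept: 1.96 × √[0.3² × (1/n_I + 1/n_H − 2/864) + 0.1² × (1/n_I + 1/n_H)]. At 95% kept (n_I = n_H = 820.8) this is ±0.012. At 10% kept (n_I = 86.4) it is ±0.064.

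A simulation with 40 patients and 100 runs per setting gave matching half-widths:

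| Isansys epochs kept | Epoch-level | Per patient, shared epochs | Per patient, own epochs |
|---|---|---|---|
| 95% | 0.277 | 0.010 | 0.012 |
| 50% | 0.277 | 0.014 | 0.024 |
| 20% | 0.277 | 0.022 | 0.043 |
| 10% | 0.278 | 0.031 | 0.064 |

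Epoch-level limits do not respond to loss. Per-patient limits do, by a factor of about five (0.064 / 0.012) when each device uses its own epochs. Whether such widening would fail the rule cannot be said, because no margin is given. Random loss leaves epoch-level limits unchanged by construction, so the table shows how the rule behaves and is no forecast of this study.

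**The case against.** Several points on the other side are fair.

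- **Yield is reported anyway.** The primary objective is descriptive and the epoch counts are its outcome, so a large loss would be visible. Reporting yield and agreement as two results is a normal structure for a device comparison, and interchangeable is common Bland-Altman vocabulary for values. This stands. However, the sentence in 2.3 names the device, not its values, and carries no condition on yield.
- **The rule is not mechanical.** Its wording is permissive and appeals to clinical interpretation. This stands too: the protocol permits the claim and does not compel it.
- **Loss can enter indirectly.** Section 2.3 plots by patient, and section 4.3 also uses whole 24-hour recordings. Such measures widen with loss, and loss concentrated in care episodes could bias them. No stated limit turns this into a failure.
- **Complete data.** Sections 3.1 and 4.5 refer to patients with complete data. If complete means full recordings from both devices, extreme loss might never reach the analysis. The term is not defined, so this neither settles the point nor removes it.
- **A yield margin may be too much for a pilot.** The documents offer no basis for a value. This is a good reason to make the margin optional.

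A reader might go further and infer that this rule is the trial's conclusion, or that it selects the device for later studies. The documents do not support either. Device choice is a separate secondary objective that also weighs cost, and staff views on usability are collected. A reader might also infer that losing data makes agreement look better. That would require the lost epochs to be the ones with the largest errors, which the documents do not show. Nor is keeping artefact epochs in the analysis a relevant comparator, since the protocol requires their removal.

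**Conclusion.** The point holds in a limited form. The only written decision rule allows a device-level claim of interchangeability from HRV differences alone, while the primary outcome has no part in it. Heavy Isansys loss would be reported and might widen per-patient or 24-hour limits, but it would not by rule prevent the claim.

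This rests on the text of section 2.3, section 2.1 and the synopsis, not on the illustration, whose SDs and random loss are assumed. The documents give no expected loss and no margin, so the chance of a misleading declaration cannot be quantified. A statistical analysis plan may add detail, but the protocol itself fixes the rule and its wording. The matter deserves correction because the change is small and alters what the study may conclude.

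**What to change.** In section 2.3 and the synopsis:

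1. Limit the agreement conclusion to: *HRV values agree when both devices give an interpretable signal.*
2. Beside every agreement result, report over the shared recording window the percentage of 5-minute epochs interpretable on each device and on both, with the within-patient difference (Holter minus Isansys) and its 95% confidence interval.
3. Reserve *interchangeable device* for the case where this yield difference also meets a margin set before analysis, if the team chooses to set one. Without a margin, only the narrower statement in item 1 is made.

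The cost is a few sentences and no new data, because epoch counts are already the primary outcome. The claim becomes narrower. A common epoch denominator must be used because maximum recording times differ (72 h against up to 5 days). The team should also confirm that interpretable means the same on both sides, since section 2.3 derives Holter HRV in the device's software and sends Isansys RR intervals through Matlab.

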4.3 Schedule of study procedure

With informed consent, the following routinely recorded clinical and laboratory data will be collected:

- Baseline demographics and comorbidities
- Administration of beta blockers or anti-arrhythmics
- Administration of sedative agents (general anaesthetics/opioids/benzodiazepines)
- Reasons for admission to ICU
- Daily biochemistry and haematology results
- Severity of illness scores, including APACHE II and daily SOFA scores
- Daily CAM ICU scores / delirium
- Daily cardiac rhythm as per nursing entry or clinical diagnosis
- Daily clinical parameters, including medications (vasopressors/ionotropes/steroids/muscle relaxants) and organ support
- Daily AKI stage, including treatment with RRT

After obtaining informed consent, continuous ECG data will be recorded using the two different devices. ECG data will then be processed to derive HRV using the methodology described by the European Society of Cardiology Taskforce guidelines.² Processing of ECG data entails checking

for and removal of extrasystole and ectopic beats with interpolation of QRS complexes as described elsewhere.² Continuous 24 hour ECG recording will then be divided into 5 minute epochs for which short term HRV values will be calculated. HRV will be calculated in the time domain, frequency domain and non-linear domains for each 5 minute epoch. Entire 24 hour ECG recordings will be used for long term HRV measures in the time domain, frequency domain and non-linear domains as described the Taskforce guidelines.² HRV data will then be analysed according to that described in the statistical methodology and analysis section. HRV data will be calculated by the Medical Engineering and Clinical Physics department at the Royal Liverpool and Broadgreen University Hospital. They will be blinded to any patient identifiable or clinical information.

Daily data will be collected until day 5 in ICU, day of discharge from ICU or day of death (depending on what occurs first). In addition, we will record ICU and hospital length of stay, ICU and hospital mortality and occurrence of arrhythmias during ICU stay, after 30 days, and after 90 days following enrollment. Data will be collected by accessing routinely available results in the patients' medical records, and if necessary, by contacting the patient's General Practitioner (GP).

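### The only categorical tests named, chi-square with Fisher's exact as fallback, ignore pairing and clustering; applied to the primary comparison of interpretable epochs, their error rate would be uncontrolled in either direction

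*Protocol*

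**What the plan says.** Section 2.3 (Trial Statistics), repeated in the Study Synopsis, gives one rule for categorical data: "Chi-square tests will be used for categorical outcomes unless assumptions of the test are found to have been violated". Fisher's exact test is the only remedy offered for such a violation. The sentence before it says that "number and proportions for categorical variables will be used for all comparisons". No paired or clustered categorical method is named anywhere in the protocol.

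The primary outcome in section 2.1 is: "Number of interpretable monitoring epochs in each HRV monitoring system after elimination of artefacts, extra beats and interference". The Synopsis adds that this outcome is to be compared between the Isansys device and the Holter monitor.

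Section 4.3 has both devices recording each enrolled patient, and says: "Continuous 24 hour ECG recording will then be divided into 5 minute epochs for which short term HRV values will be calculated". Sections 1 and 6.2 give a 72-hour Holter recording.

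For the devices, section 2.3 says: "Comparison between devices will be assessed by Bland-Altman methodology". It describes this for HRV measures: differences are "plotted against the average value for each HRV measure for individual patients". For continuous variables it offers parametric or nonparametric methods, without saying whether they are paired.

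**The concern.** Chi-square and Fisher's exact test both require independent observations. Here the two devices observe the same patient at the same time, and each patient contributes hundreds of epochs. The protocol foresees that the chi-square assumptions may fail, but the remedy it names rests on the same independence. Fisher's test helps with small expected counts; it does nothing for pairing or clustering.

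This matters most for the primary outcome. Bland-Altman is described for HRV measures, and whether an epoch is interpretable is not an HRV measure. An analyst who wants to compare interpretable proportions between devices finds only chi-square and Fisher among the named methods for proportions. Depending on how the data behave, the result could be a spurious device difference or a real one missed, in a study meant to guide the choice of device for later research.

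**Working it through.** The protocol states no alpha, effect size or interpretable rate, so there is no figure of its own to reproduce.

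**Inputs from the protocol.** Five-minute epochs (section 4.3); 24-hour recordings (section 4.3) and a 72-hour Holter recording (sections 1 and 6.2); 30 patients (Synopsis, section 4.5) or 40 (section 3.1).

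**Epoch counts.** 24 x 60 / 5 = 288 per day; 72 x 60 / 5 = 864. Pooled per device: 30 x 288 = 8,640 up to 40 x 864 = 34,560.

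**Assumed inputs.** Two-sided 5% level; 80% interpretable in a typical patient; patient SD 1 on the logit scale; no true average device difference. Two quantities are varied: the device-by-patient SD (each device's own shift in a given patient) and the share of epochs in which one disturbance hits both devices.

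**Simulated false-positive rate of pooled-epoch chi-square** (4,000 runs per setting, 30 and 40 patients):

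| Device-by-patient SD | Shared epochs | 288 epochs | 864 epochs |
|---|---|---|---|
| 0 | none | 3.4-3.5% | 3.4-3.7% |
| 0 | half | 0.2-0.3% | 0.2-0.3% |
| 0 | 90% | about 0 | about 0 |
| 0.1 | half | 3.5-4.0% | 14.1-14.5% |
| 0.2 | none to 90% | 16-24% | 40-43% |
| 0.5 | none or half | 56-57% | 72-74% |

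A paired t test on per-patient proportions stays at 4.4-5.6% in every setting. A second simulation (2,000 runs, 30 patients x 864 epochs, patient SD 0.8) gives 4%, 20%, 54% and 75% at SDs of 0, 0.1, 0.25 and 0.5, with the paired test at 5-6%.

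**Hand check.** The true standard error of the mean device difference is s/√N, where s is the SD of the per-patient differences. Chi-square uses √(2p(1-p)/(Nm)). The actual level is 2[1 - Φ(1.96 x naive SE / true SE)]. Take N = 30 and p = 0.8.

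- m = 864, SD 0.5, s = 0.117: true SE 0.117/√30 = 0.0214; naive SE √(0.32/25,920) = 0.00351; ratio 6.08; level 0.75.
- m = 864, SD 0.1, half shared, s = 0.027: true SE 0.00493; ratio 1.40; level 0.16.
- m = 288, SD 0.1, half shared, s = 0.033: true SE 0.00603; naive SE √(0.32/8,640) = 0.00609; ratio 0.99; level 0.05.
- m = 864, SD 0, half shared, s = 0.013: true SE 0.00237; ratio 0.68; level 0.004.

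These run slightly above the simulation, because with a patient SD of 1 logit the average proportion is below 0.8 and the naive SE is a little larger.

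The 4% at 288 epochs depends on the sharing. Without it, s² = 0.032² + (0.033² - 0.023²) = 0.00158, so s = 0.0398, the ratio is 1.19 and the level is about 0.10. The same step at 864 epochs gives s² = 0.019² + (0.027² - 0.013²) = 0.00092 and a level of about 0.21. That explains the gap between 14% and 20% at SD 0.1.

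**Design-effect view.** DE = 1 + (m - 1) x ICC, where the ICC is for device within patient. At ICC 0.01, DE = 3.87 (m = 288) or 9.63 (m = 864), and the actual level is 0.32 or 0.53. At ICC 0.001 it is 0.08 or 0.15.

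**One yes/no result per patient and device** (80% positive). Unpaired chi-square has a level of 1.9-2.0% at within-patient correlation 0.3, 0.7-0.8% at 0.5, and about 0 at 0.8. McNemar's test stays between 1.2% and 4.7%.

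**Bland-Altman (secondary).** Assume SDs of the differences of 3 ms between and 10 ms within patients, with epochs independent within a patient. Limits from patient means are ±1.96 x √(9 + 100/864) = ±5.9 ms. Limits for a single epoch are ±1.96 x √(9 + 100) = ±20.5 ms.

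**The case against.** A reader might infer that the protocol prescribes chi-square for the device comparison, and that false-positive device differences are therefore likely because the devices share patients. The documents do not support this. The chi-square sentence is generic and names neither devices nor epochs. It also fits one-per-patient variables that the protocol collects, such as mortality and occurrence of arrhythmia. Device comparison is assigned to Bland-Altman, a paired method. The primary outcome is worded as a number, so it could go to the parametric or nonparametric methods, which do not exclude a paired t or signed-rank test.

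The direction is also not given. Ignoring positive pairing alone makes chi-square conservative. Inflation needs pooled epochs and device-by-patient variation together, and the protocol gives no figure for the latter. All of this stands, and so the point is conditional.

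It can further be said that this is a pilot with a descriptive primary objective, that no alpha or hypothesis is stated, and that interchangeability is judged on limits of agreement. That lowers the stakes of any single p-value. It does not make the named fallback suitable, nor does it supply a paired method for the primary comparison in the Synopsis.

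On Bland-Altman, section 2.3 does not say whether epochs are averaged or pooled, and whole-recording measures also exist. The choice of variant could be left to a statistical analysis plan, so this part is secondary.

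**Conclusion.** The concern holds in conditional form. The protocol commits to a specific categorical test and a specific remedy, both of which assume an independence that the design lacks. If they are applied to interpretable epochs, the error rate is uncontrolled. At a nominal 5% it can fall to about zero when the devices share disturbances and do not vary by patient. With pooled epochs and 864 per patient, it can rise to about 14-20% at a device-by-patient SD of 0.1 logit and 72-75% at 0.5. With 288 epochs, an SD of 0.1 gives about 4% when half the epochs are disturbed on both devices, and up to about 10% when none are.

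The interpretable rate and all SDs are assumptions. The result is much the same for 30 or 40 patients. The calculations do not show that a false device difference is likely in this study; they show that the named tests give no protection either way, while a paired patient-level test holds close to 5% throughout.

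**What to change.** In section 2.3 and the Synopsis:

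- State that the patient is the unit of analysis for the device comparison of interpretable epochs.
- For each patient and device, compute the proportion of epochs that are interpretable, over a recording window common to both devices.
- Report the mean within-patient difference with a 95% CI, using a paired t or Wilcoxon signed-rank test, or a GEE or mixed model clustered by patient.
- Restrict chi-square and Fisher's exact test to comparisons of independent, one-per-patient variables. If a single yes/no result per patient is compared between devices, use McNemar's test.
- Where five-minute values enter the Bland-Altman analysis, use repeated-measures limits of agreement with between- and within-patient components.

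The cost is revised wording and slightly more analysis work. Where epochs would otherwise have been pooled, the intervals will be wider. No change to recruitment, recording or data collection is needed.
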